• Blood Sample - Blood samples will be taken from a vein by the P.I., phlebotomist, or research assistant that is certified in drawing blood. At the preliminary visit, up to 18 ml of blood (approximately 1-2 tablespoons) will be taken to test for blood counts, the amount of sugar in the blood and certain hormones. For **ADULTS**: Up to 75 ml of blood (approximately 4 - 5 tablespoons) will be taken during each experimental day (approximately 44 ml pre- treatment and 31 ml post-treatment). This amount is less than 1/5 of the amount that is withdrawn during a normal blood donation (500 ml or 15 fluid ounces). For **CHILDREN**: Up to 50 ml of blood (approximately 3 – 4 tablespoons) will be taken during each experiment and 20 ml post-treatment). This amount is about 1/10 of the amount that is withdrawn during a normal blood donation (500 ml or 15 fluid ounces). To prevent the number of needle sticks for the blood draws, a sterile plastic catheter tube will be placed for the duration of experimental day 2. We will use this blood to test for blood fat (cholesterol), blood sugar, and the concentration of certain hormones. **NOTE**: Healthy controls will not receive treatment, and therefore the blood draw amount will be the "pre-treatment" volume listed above.

• Arterial Stiffness Evaluation (PWV/PWA) – A device will be used to measure how fast blood travels. This test is called pulse wave velocity or PWV. How fast blood travels is also a measure of how stiff the arteries are. Stiff blood vessels/arteries are linked to high blood pressure and heart disease. To start the test, a blood pressure cuff is placed on the subject's arm and leg. A pen-like device is gently applied on the carotid artery (neck) and the radial artery (wrist) to record how fast the blood flows between each of the points.

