• Arterial Function (FMD) - Measurements of arterial health will be completed using ultrasound technology to detect how well the artery expands with changes in blood flow. This technique is used to characterize the health of arteries. The subject will lie down for 20 minutes to become fully rested. After the 20 minute resting phase, a water based gel will be put on the ultrasound transducer and then put on the subject's skin. The gel helps achieve better pictures of the artery. We will then test the artery function. After baseline measurements, a blood pressure cuff placed around the forearm will be inflated to 250 mm Hg to stop blood flow for 5 minutes. Data will be recorded for 2 minutes following the

release of the cuff. The health of the artery will be expressed as a percentage of the artery expansion with the increased blood flow, compared to the resting diameter.

• Nitroglycerin spray (EID) – Nitroglycerin is a fast acting drug that causes blood vessels to dilate (or get bigger). After we perform the post FMD test and while the subject is still laying down, [name] or his research associate will spray one dose (0.4 mg/spray) of nitroglycerin under the tongue. We will continue to monitor heart rate, blood pressure, and the blood vessel through ultrasound for up to 15 minutes. This test measures arterial health and the maximal capability of the artery to expand.

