• Continuous Glucose Monitoring (CGM) -- For patients that use a Dexcom for clinical evaluation of continuous glucose monitoring, we will ask him/her for permission to share their data using the Clarity software provided by Dexcom. To do this, we will send them a link that integrates

their individual continuous glucose data with the Clarity software to give us real time access of the data throughout the duration of the study. The Clarity software is HIPAA compliant, and patients using this software have already agreed to share their health information with Dexcom. Our study team will discontinue our access to the patient's data through the Dexcom Clarity app within one week of the participant's final visit. This will remove all future access to the participant's data. Access can only be granted if the participant re-shares their data with our research team.

• Randomized Treatments – After enrollment, the subject will be randomized to receive either an antioxidant cocktail, resveratrol, or a placebo. The antioxidant cocktail is comprised of over the counter vitamins (vitamin C 1,000 mg, vitamin E 600 IU, and alpha lipoic acid 600 mg) that will be given in two doses, 30 minutes apart. Resveratrol (1500 mg of trans-resveratrol) is a natural polyphenol that is found in multiple food sources. Nicotinamide riboside (1,000 mg) is an over-the-counter supplement. The placebo will consist of lactose or sucrose (sugar pills).

b. Describe and explain the study design:

Brachial artery flow-mediated dilation and a small blood sample (10 ml) will be performed in the girls/women during the menses (days 1-5 of the menstrual cycle) and late follicular (day 12-14) phases, whereas the men will be studied twice at the same frequency as the girls/women. Participant subject medical information will be assessed during the first visit.

c. Describe the procedures performed to lessen the probability or magnitude of risks:

All procedures in this study have been routinely performed in research studies in the past and are of low risk to participants. [name] is a trained clinical exercise physiologist with experience performing high-risk exercise in patient populations. In an effort to maintain subject safety but also investigate endothelial dysfunction from smooth muscle dysfunction, we will administer nitroglycerin only in adults, and only one time at baseline.

d. Describe the duration of an individual subject's participation in the study and the time involved:

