Participation in the study will involve 3 testing visits to the GPI (one preliminary testing visit at the beginning of the study and 2 experimental that for females are based on their menstrual cycle. Prelim visit will take approximately 2 hours, experimental visits 1 and 2 will last approximately 5 hours. Those subjects serving as controls will not receive randomized treatments. Participants may or may not be asked to conduct all visits or even take treatments and/or perform all procedures during each experimental testing day depending on time and availability. If a subject recently participated in a study with us that involved these same tests, we may use data from that study to avoid redundant testing measures.

7. Data and Specimen Management

Thi gen	cribe the data analysis plan, including any statistical procedures: s is simply a pilot experimental study. Therefore, descriptive statistics will be erated and paired t-tests and linear regression analyses will be performed ong the dependent variables; FMD, hormones, and lipids.	□ N/A			
b. Wh	en applicable, provide a power analysis:	□ N/A			
	re is no formal power calculation because this proposal is designed just btain preliminary data for a grant submission.				
c. Des	cribe how data and specimens will be handled:	□ N/A			
i.	What information will be included in that data or associated with the specin	mens?			
	All data sheets and stored specimens will be de-identified.				
ii.	Where and how data and/or specimens will be stored?				
	Data are stored in subject folders, specimens are stored de-identified in -80) freezers			
iii.	How long will the data and/or specimens be stored?				
	Click here to enter text.				
iv.	Who will have access to the data or specimens?				
	Only investigators that will be involved with the data will have access to the specimens	e data or			
V.	Who is responsible for receipt or transmission of the data and/or speciment	s?			
	[name] is responsible				
vi	How will data and/or specimens be transported?				
	Specimens will be transported according to the biosafety procedures and				
	regulations				

8. Provisions to Monitor the Data to Ensure the Safety of Subjects

This study involves no more than minimal risk study and this section is not required. \Box N/A

The plan might include establishing a data monitoring committee and a plan for reporting data monitoring committee findings to the IRB and the sponsor.

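### Section 6d lets visits be skipped and earlier data be reused with no condition on cycle phase or treatment state, so the paired phase contrast in girls/women can lose pairs or be diluted

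*Combined protocol and SAP*

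**What the plan says.** - **Design (6b).** In girls/women, brachial FMD and a 10 ml blood sample are taken "during the menses (days 1-5 of the menstrual cycle) and late follicular (day 12-14) phases".
- **Visits (6d).** After a preliminary visit there are "2 experimental that for females are based on their menstrual cycle".
- **Omission (6d).** "Participants may or may not be asked to conduct all visits or even take treatments"; procedures within an experimental day may be left out too. The stated reason is time and availability.
- **Reuse (6d).** "If a subject recently participated in a study with us that involved these same tests, we may use data from that study". The stated purpose is to avoid redundant measures.
- **Treatment state (6a, Blood Sample).** Adults' blood on each experimental day is split into "44 ml pre- treatment and 31 ml post-treatment". A post-treatment volume is also given for children. Healthy controls are untreated and give only the pre-treatment volume.
- **Analysis (7a, 7b).** The study "is simply a pilot experimental study", and "paired t-tests and linear regression analyses will be performed" on FMD, hormones and lipids. Section 7a does not say which values form the pair, what happens when one half is missing, or how a reused value is treated. Section 7b gives no power calculation.
- **Oversight (8a, 8b).** Protocol compliance checks are planned.

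**The concern.** Aim 1 asks whether estrogen contributes to endothelial dysfunction in premenopausal women with diabetes. The design answers it by timing: the same person is measured at menses and again in the late follicular phase. An FMD, hormone or lipid value informs that contrast only if its phase is known and it was taken untreated.

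The two permissions in 6d act on the contrast in different ways.

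- **Reuse** could put a value from another phase, or one taken after treatment, into one half of a pair. A wrong-phase value shrinks the mean difference. A post-treatment value adds whatever the treatment did.
- **Omission** adds no wrong value. It can leave a participant with one half of a pair, and a paired t-test then discards that half.

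Because 7b says that the study is meant to supply preliminary data for a grant submission, a diluted difference could be carried into the sample size of a later trial and inflate it.

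**Working it through.** **No plan figure to reproduce.** The documents give no effect size, standard deviation, significance level, expected rate of skipped visits or number of reused values. The check is therefore a reading of the text plus illustrations. Every rate and correlation below is assumed.

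**1. The text.** Section 6d limits reuse in two ways: the earlier participation was recent, and the tests were the same. Phase and treatment state are not mentioned, and *recently* has no length. Section 6b fixes the phases for this study but does not address values imported from another one. For blood, 6a shows that the same test can exist both before and after treatment on one day, so naming the test does not settle the treatment state.

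**2. Skipped experimental visits.** Let *q* be the share of participants with the first experimental visit only, and *ρ* the correlation between a person's two values. Equal variances are assumed, and visit 1 is taken as menses because the ovulation kit is handed out at its end to time the later visit.

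- Paired t-test: a share 1 − *q* of pairs remains, so the interval widens by the factor 1/√(1 − *q*).
- Linear mixed model (generalised least squares, variances known): the variance of the phase difference relative to complete data is 1 + *q*(1 + *ρ*)/[2(1 − *q*)]. The interval factor is its square root.

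| *q* | Paired t-test | Mixed model, ρ = 0.3 | ρ = 0.5 | ρ = 0.7 |
|---|---|---|---|---|
| 10% | 1.054 | 1.035 | 1.041 | 1.046 |
| 30% | 1.195 | 1.131 | 1.150 | 1.168 |

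Example, *q* = 0.30 and *ρ* = 0.5: 1 + 0.30 × 1.5/(2 × 0.70) = 1.321, and √1.321 = 1.150. For the paired test, 1/√0.70 = 1.195.

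At *q* = 5% and 20% the paired t-test factor is 1.026 and 1.118. The model recovers part of the loss, not all of it, so keeping both visits does more than changing the analysis.

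**3. Reused wrong-phase values.** Let *f* be the share of pairs in which one half is replaced by a value that carries none of the phase contrast. The mean paired difference is multiplied by 1 − *f*. With the standard deviation unchanged, a later sample size based on it scales as 1/(1 − *f*)².

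| *f* | Mean difference × | Later sample size × |
|---|---|---|
| 5% | 0.95 | 1.11 |
| 10% | 0.90 | 1.23 |
| 20% | 0.80 | 1.56 |

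Mixing true and null pairs also raises the standard deviation a little. With an assumed standardised paired difference of 0.5, the variance becomes 1 + *f*(1 − *f*) × 0.25. The last two factors are then 1.0225/0.81 = 1.26 and 1.04/0.64 = 1.63. A mistimed value that keeps part of the contrast dilutes less than the table shows.

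**4. Reused post-treatment values.** One half of the pair then contains the treatment effect, so the difference is the phase effect plus or minus that effect. The direction is unknown and no size can be given.

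**The case against.** The other side has several fair points.

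- **A strict reading closes most of the reuse gap.** A test is redundant only if an equivalent value already exists. Read with 6b and with visits tied to the cycle, that excludes out-of-phase values, and the phase effect of reuse is then zero. This stands as a reasonable reading. It is not written down, and it does not settle treatment state or the length of *recently*.
- **Compliance checks have a standard for phase.** An imported value standing in for a visit can be checked against the 6b windows. That also stands. For treatment state and data age there is nothing to check against.
- **The pair is implied.** Aim 1 and 6b make menses versus late follicular the natural pair. Naming it in 7a supplies a missing detail and does not correct an error.
- **The loss from skipping is modest.** If scheduling is the only reason, skipped visits cost precision without bias. At 10% one-visit participants, the mixed model reduces the widening only from 5.4% to between 3.5% and 4.6%.
- **It is a pilot.** That explains the absent power calculation and lowers the priority.

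Some stronger readings are tempting, but the documents do not support them.

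- A reader might infer that mismatched values are in use, or that earlier studies gave treatment. Neither is stated; 6d is a permission.
- A reader might infer that pairs will be incomplete. Omission is allowed, not required, and skipping only the preliminary visit breaks no pair.
- A reader might infer that FMD, like blood, is measured before and after treatment on each day, which would give many possible pairs. Section 6a places nitroglycerin "After we perform the post FMD test and while the subject is still laying down", but 6c restricts nitroglycerin to one administration at baseline in adults, so *post* need not mean post-treatment. The pre/post split is secure for blood only.
- A reader might infer that skipped treatments spoil a randomised comparison. Section 7a names no such comparison.

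**Conclusion.** The point holds as an unguarded permission, not as a demonstrated error. Section 6d lets experimental visits be skipped and lets earlier values be reused without a phase or treatment-state condition, while the planned paired t-test needs both halves of a correctly timed pair. Pairs can be lost, and a mismatched reused value could dilute or distort the difference.

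The size cannot be derived from the documents. For scale only, 30% one-visit participants would widen the paired t-test interval by about 20%, against about 13–17% with a mixed model at correlations of 0.3–0.7. Replacing one half in 10% of pairs with a value carrying no contrast would shrink the mean difference to 0.90 of its true value. These figures rest on assumed rates, equal variances and, for the mixed model, missing visits unrelated to the unseen values.

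The change is worth making because it is cheap. Its priority is modest.

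**What to change.** 1. **Reuse (6d).** Allow earlier FMD, hormone and lipid values only if they were taken untreated, are within a stated age and, in girls/women, have documented timing in the phase that the visit requires. Flag reused values in the data file and repeat the analysis without them. Phase-independent measures such as DXA can stay reusable.
2. **Skipped measures (6d).** Make FMD and the hormone sample at both experimental visits the last measures dropped when time is short, subject to the withdrawal provisions in Section 9.
3. **Analysis (7a).** State that the Aim 1 contrast in girls/women is pre-treatment menses versus pre-treatment late follicular. Fit a linear mixed model with a participant random effect and a phase fixed effect, so that one-visit participants contribute. Report the number of complete pairs.

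**Cost.** The change needs wording in two sections and one flag in the data file; the model needs no extra data. The downside is less scheduling freedom and some repeat testing of returning participants whose earlier values lack a documented phase or treatment state. At most that is part of a visit of about 5 hours and up to 75 ml of blood in adults or 50 ml in children per experimental day. Continuing to accept documented, untreated values limits this burden.

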Study Title: Estrogen mediated vascular endothelial dysfunction in Diabetes Brief Title: Estrogen and Diabetes Clinical Trials: NCT03436992 Document Version Date: 11.14.22 Principal Investigator: [name]

1. Objectives

Describe the purpose, specific aims, and hypothesis:

The purpose of this proposal is to investigate whether or not estrogen contributes to vascular dysfunction in premenopausal women with diabetes. Specific Aim 1. To test the hypothesis that estrogen contributes to vascular endothelial dysfunction in premenopausal women with diabetes.

2. Background

Describe the background and rationale for the study:

There is an extensive body of knowledge that indicates premenopausal women have an innate protection from cardiovascular disease and estrogen is what contributes to this protection. In contrast to these protective findings in humans, using an animal model, estrogen in diabetes has been indicated to contribute to vasoconstriction.

3. Inclusion and Exclusion Criteria

List the inclusion/exclusion criteria: Inclusion criteria:

- Both boys/men (with T1DM) and girls/premenopausal women (with or without T1DM)
- \geq 7 years of age
- Normal menstrual cycle interval of 25-35 days for at least 3 previous cycles
- All races
- Clinical diagnosis of insulin-dependent type 1 diabetes (patients only)

Exclusion criteria:

- Clinical diagnosis of hepatic, cardiovascular, or renal disease
- Uncontrolled Diabetes (HbA1c > 12%)
- Diabetic complications (i.e. macrovascular, microvascular, or autonomic)
- Proteinuria
- Uncontrolled Hypertension (>140/90 mm Hg on therapy)
- Pregnancy
- Oligomenorrhea
- Direct vasoactive medications (i.e. nitrates)
- Anti-estrogens (i.e. SERMs)
- Polycystic ovarian syndrome (defined by NIH guidelines hyperandrogenic anovulation)
- Undetectable Anti-Mullerian Hormone (AMH) following screening

4. Number of Subjects/Records/Samples Collected

Indicate the total number of subjects to be accrued/records reviewed/samples collected across all sites: 198 total subjects to be accrued

5. Recruitment Methods

Describe when, where, and how potential subjects will be recruited:

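### Section 7a names no test of whether the menses-to-late-follicular change in FMD differs between women with and without T1DM, and does not say which groups enter the paired t-tests

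*Combined protocol and SAP*

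**What the plan says.** - **Aim (Section 1).** "To test the hypothesis that estrogen contributes to vascular endothelial dysfunction in premenopausal women with diabetes". No comparator is named.
- **Rationale (Section 2).** Estrogen is described as protective in premenopausal women generally. Then: "In contrast to these protective findings in humans, using an animal model, estrogen in diabetes has been indicated to contribute to vasoconstriction".
- **Groups (Section 3).** Males with T1DM, and females either with or without T1DM. Section 4 gives a total of 198 with no split by group.
- **Measurements (Section 6b).** FMD in girls and women "during the menses (days 1-5 of the menstrual cycle) and late follicular (day 12-14) phases". The men are studied twice on a matching schedule.
- **Visit order (Section 6a, Ovulation Predictor Kit).** The kit is handed out at the end of experimental day 1 and is used to time visit 2 to high estrogen. Low estrogen therefore comes first and high estrogen second.
- **Treatment (Section 6d).** "Those subjects serving as controls will not receive randomized treatments".
- **Analysis (Section 7a).** Descriptive statistics, and "paired t-tests and linear regression analyses will be performed" among FMD, hormones and lipids. There is no analysis set, regression covariate, group term, interaction or between-group test.

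**The concern.** The Background and the recruitment of untreated healthy women both point to a comparative question: does FMD respond differently to the high-estrogen phase when diabetes is present? The quantity that answers it is a difference between two within-woman changes. A paired t-test estimates only one change.

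This leaves three ways to run the stated test, none of which answers that question:

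1. **T1DM women only.** Phase and visit order coincide, so a fall in FMD could come from estrogen acting differently in diabetes, from a cycle effect that any woman shows, or from repeat testing.
2. **Each group separately.** This invites comparing one p-value with another, which is not a test that the changes differ.
3. **All women together.** The estimate moves toward the healthy women's change.

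At stake are the meaning of a positive result and the use made of the healthy controls, who have no stated role in any test.

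**Working it through.** **Inputs.** The plan gives no alpha, power, effect size, SD or group split, so there is no figure of its own to reproduce. Everything below is assumed except the total of 198: three equal groups (198/3 = 66 per group, hence 132 women), SD of the within-woman FMD change of 2, 3 or 4 points, two-sided alpha 0.05, normal approximation.

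**1. T1DM women alone, when both groups truly fall by 1 point.** The between-group difference is −1 − (−1) = 0. The standard error is SD/√66 = 0.246, 0.369 or 0.492, so 1/SE = 4.06, 2.71 or 2.03. The chance of significance is 0.98, 0.77 or 0.53. A positive result is thus likely with nothing particular to diabetes.

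**2. Separate tests, same truth.** With p the power from step 1, the chance of significance in T1DM women but not in healthy women is p(1 − p) = 0.02, 0.18 or 0.25. That pattern would look like a diabetes effect.

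**3. Pooled test, if it were used.** With w the T1DM share, the pooled mean is w·d_T + (1 − w)·d_H, and the variance is SD² + w(1 − w)(d_T − d_H)². N = 132.

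| Change in T1DM / healthy | T1DM share | Pooled mean | Power at SD 2, 3, 4 |
|---|---|---|---|
| −1 / +1 | 1/2 | 0.00 | 0.05, 0.05, 0.05 |
| −1 / +1 | 2/3 | −0.33 | 0.41, 0.23, 0.15 |
| −1 / 0 | 1/2 | −0.50 | 0.80, 0.47, 0.30 |
| −1 / +2 | 1/2 | +0.50 | 0.63, 0.40, 0.27 |

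Cancellation is complete only when w·d_T = −(1 − w)·d_H. In the other rows the effect is diluted or, in the last, reversed in sign.

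**4. The between-group contrast.** The standard error is SD·√(2/66). The difference detectable with 80% power is (1.96 + 0.84)·√(2/n) SDs: 0.49 at n = 66 per group, 0.69 at 33 and 0.89 at 20.

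- For a 2-point difference (−1 against +1), power at 66 per group is above 0.99, 0.97 and 0.82. The n per group for 80% power is 16, 36 and 63.
- For a 1-point difference (−1 against 0), power at 66 per group is 0.82, 0.48 and 0.30. The n per group for 80% power is 63, 142 and 252.

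The single-group change detectable at n = 66 is 2.80/√66 = 0.34 SD, so the contrast is less precise by a factor of √2.

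**The case against.** Much can be said for the plan, and several stronger readings that a reader might infer are not supported.

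- **That the plan cannot show a diabetes-specific effect.** Section 7a includes linear regression with unstated terms. Regressing the FMD change on diabetes status would be exactly the needed test. The fault is that it is not specified, not that it is impossible.
- **That the paired test pools the women and cancels the effect.** No section says the groups are pooled. Aim 1 concerns women with diabetes, so a test within T1DM women is at least as natural a reading.
- **That Aim 1 itself claims a diabetes-specific effect.** It does not; that reading comes from the Background and the control group. A cycle effect shared by both groups would not contradict the aim as worded.
- **That opposite signs are predicted for FMD.** Section 2 sets general cardiovascular protection in humans against vasoconstriction in an animal model. It predicts no direction for the healthy women's FMD change. The −1/+1 case is an illustration.
- **That the data needed are certain to exist.** Section 6d allows visits, treatments and procedures to be skipped, and data from an earlier study to be reused.

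Two further points also stand. The T1DM men, who have no menstrual cycle and are tested twice, can expose a repeat-visit effect, though not an ordinary cycle effect. And since only T1DM participants are treated, a lasting effect of treatment given at visit 1 would mix diabetes with treatment in the proposed contrast; the plan does not say whether this can occur.

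The pilot label in Sections 7a and 7b explains why there is no power calculation. It does not explain why the contrast that would use the controls is not named.

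**Conclusion.** The point holds as a gap in specification. Section 7a names no diabetes-by-phase comparison and does not say who enters the paired tests, so the stated test does not separate an estrogen effect particular to diabetes from a cycle or visit-order effect. That follows from the text and the fixed visit order, without any assumed number.

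Its size depends on assumptions. With 66 women per group and an equal 1-point fall, the T1DM-only test is positive in 53% to 98% of studies, and separate tests give a misleading split in 2% to 25%. The harm from pooling is conditional: it arises only if pooling is done, and full cancellation needs offsetting weighted changes. The plan should be amended on this point, but the design can already supply the contrast wherever both visits are completed.

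**What to change.** In Section 7a:

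1. Make the main Aim 1 contrast the within-woman change in pre-treatment FMD (late follicular minus menses), regressed on diabetes status among women with both visits. A diabetes-by-phase term in a repeated-measures model is an alternative.
2. Report the paired change with its confidence interval separately for T1DM women, healthy women and T1DM men, the men serving as a non-cycling check on visit effects. State that women with and without T1DM are not pooled in the paired test.
3. Check that visit-1 treatment does not affect visit-2 pre-treatment FMD, for example by repeating the contrast with only placebo or untreated T1DM women.
4. State the intended split of the 198 and report how many women in each group have paired data.

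**Cost.** A few sentences and no new measurements. The contrast is less precise than a single-group change, and missed visits allowed by Section 6d reduce the number of pairs. The check in item 3 is weaker still: if, say, 22 of 66 T1DM women were on placebo (assumed), the detectable difference against 66 healthy women would be 2.80·√(1/22 + 1/66) = 0.69 SD instead of 0.49 SD. It should be read as supportive.
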